7.4 EXAMINATION SCHEDULE

Evaluation	Subjects who did not previously participate in CSP-037-MX or Former CSP-037-MX subjects with fellow eye (CSP-037-MX non-study eye) enrolled	Former CSP-037-MX subjects with only former CSP-037-MX study eye enrolled
Preoperative	Day -60 to Day -1	NA
Operative	Day 0, day of surgery	NA
Postop Day 1	Days 1 to 2 postop	NA
¹	Days 7-14 postop	NA
Postop Week 3	Days 17 to 30 days postop: Adjustment #1	Days 17 to 30 days postop: Adjustment #1
Adjustment #2, if needed	2 to 7 days post Adjustment #1	2 to 7 days post Adjustment #1
Adjustment #3, if needed	2 to 7 days post Adjustment #2	2 to 7 days post Adjustment #2
Lock-in #1	2 to 7 days post final adjustment	2 to 7 days post final adjustment
Lock-in #2, if needed	2 to 7 days post lock-in #1	2 to 7 days post lock-in #1
Post Lock-in	7 to 14 days post final lock-in	7 to 14 days post final lock-in
Postop Month 3	Days 90 to 150 postop	Days 90 to 150 postop
Postop Month 6 or later	Days 180 to 400 postop	Days 180 to 400 postop

¹ Subgroup of eyes determined by the principal investigator

Unscheduled visits falling outside the designated ranges for scheduled visits will be considered “interim” visits for data recording purposes. A report form will be completed for interim visits on the study eye.

7.5 CLINICAL PARAMETERS

4. Demographics
5. Ocular History
6. History of Medications
7. Subjective symptoms/complaints (subject reported)
8. Ocular Biometry: Axial length + Anterior Chamber Depth
9. Corneal Topography
10. Autorefraction
11. Undilated photopic pupil diameter
12. Corneal Keratometry
13. Vision Quality Measurement
14. Anterior Segment OCT
15. Posterior Segment SD-OCT
16. Monocular uncorrected distance visual acuity (UCDVA)
17. Binocular uncorrected distance visual acuity
18. Manifest Refraction
19. Monocular best corrected distance visual acuity (BCDVA)
20. Ocular Dominance Test
21. Depth of focus testing
22. Monocular distance corrected intermediate visual acuity (DCIVA)
23. Monocular distance corrected near visual acuity (DCNVA)
24. Monocular uncorrected near visual acuity (UCNVA)
25. Binocular uncorrected near visual acuity
26. Binocular uncorrected intermediate visual acuity
27. Monocular uncorrected intermediate visual acuity (UCIVA)
28. In-office Erythropsia assessment
29. City University Color Test
30. Monocular Distance corrected contrast sensitivity: Mesopic/Photopic with+ w/o glare
31. Intraocular pressure
32. Slit lamp exam
33. Fundus Exam
34. Aberrometry
35. Dilated pupil diameter

36. Adverse Event

Table 1. Schedule of Visits and Clinical Parameters

Visits	Preop*	Operative*	Postop Day 1*	[REDACTED]**	Postop Week 3	Adjustment #2 (if needed)	Adjustment #3 (if needed)	Lock-in #1	Lock-in #2 (if needed)	Post Lock-in	Postop Month 3	Postop Month 6 or later	Unscheduled Visit ³
[REDACTED]				X ¹	X ^{1,1}					X ¹	X ¹	X ¹	
[REDACTED]				X	X	X	X	X	X	X	X	X	
[REDACTED]			X ²	X ²	X ²	X ²	X ²	X ²	X ²				
Demographics	X												
Ocular History	X				X ⁴								
History of Medications	X	X	X	X	X	X	X	X	X				
Subjective Symptoms/Complaints			X	X	X	X	X	X	X	X	X	X	X
Ocular Biometry (ACD + Axial Length)	X			X	X					X	X	X	
Corneal Topography	X			X	X					X	X	X	
Autorefraction				X	X	X	X	X	X	X	X	X	
Undilated photopic pupil diameter				X ²	X ²					X ²	X ²	X ²	
Corneal Keratometry	X			X	X					X	X	X	

¹ Only performed on subjects with both eyes enrolled and successfully implanted

^{1,1} Only performed on subjects with both eyes enrolled and successfully implanted and subject did not have an [REDACTED] visit

² May be performed on a subgroup of subjects as described in section 7.3.2.2 of the protocol

³ Tests indicated with an “X” must be performed at each unscheduled visit. Other tests may be conducted based on the investigator’s assessment of the subject.

⁴ Only required for subjects who previously participated in RxSight’s CSP-037-MX study

*Visits only required for subjects who did not previously participate in RxSight’s CSP-037-MX study

**Subgroup of eyes based on decision made by Principal Investigator

Visits	Preop*	Preop*	Operative*	Postop Day 1*	Postop Day 1*	Postop Week 3	Postop Week 3	Adjustment #2 (if needed)	Adjustment #3 (if needed)	Lock-in #1	Lock-in #2 (if needed)	Postop Month 3	Postop Month 3	Postop Month 6 or later	Unscheduled Visit ³
Visits	Preop*	Operative*	Operative*	Postop Day 1*	Postop Day 1*	Postop Week 3	Postop Week 3	Adjustment #2 (if needed)	Adjustment #3 (if needed)	Lock-in #1	Lock-in #2 (if needed)	Post Lock-in	Post Lock-in	Postop Month 6 or later	Unscheduled Visit ³
Anterior Segment OCT				X	X	X	X	X	X	X	X	X	X	X	
Posterior Segment SD-OCT					X ²	X ^{2, 5}					X ²				
Vision Quality Measurement				X	X	X	X	X	X	X	X	X	X	X	
Monocular Uncorrected Distance Visual Acuity (UCDVA)	X			X	X	X	X	X	X	X	X	X	X	X	X
Binocular Uncorrected Distance Visual Acuity					X ¹	X ^{1, 1, 2}					X ^{1, 2}	X ^{1, 2}	X ^{1, 2}		
Manifest Refraction	X				X	X	X	X	X	X	X	X	X	X	
Monocular Best Corrected Distance Visual Acuity (BCDVA)	X				X	X	X	X	X	X	X	X	X	X	
Ocular Dominance Test	X				X	X ⁵									
DOF Testing					X ²	X ^{2, 5}			X ²		X ²	X ²	X ²		
Monocular Distance Corrected Intermediate Visual Acuity					X ²	X ^{2, 5}			X ²		X ²	X ²	X ²		
Monocular Distance Corrected Near Visual Acuity					X ²	X ^{2, 5}			X ²		X ²	X ²	X ²		

¹ Only performed on subjects with both eyes enrolled and successfully implanted

^{1,1} Only performed on subjects with both eyes enrolled and successfully implanted and subject did not have an visit.

² May be performed on a subgroup of subjects as described in section 7.3.2.2 of the protocol

³ Tests indicated with an "X" must be performed at each unscheduled visit. Other tests may be conducted based on the investigator's assessment of the subject.

⁴ Only required for subjects who previously participated in RxSight's CSP-037-MX study.

⁵ Only performed on subjects who did not have an [REDACTED] visit.

*Visits only required for subjects who did not previously participate in RxSight's CSP-037-MX study.

** Subgroup of eyes based on decision made by Principal Investigator.

Visits	Preop*	Operative*	Postop Day 1*	[REDACTED] *	Postop Week 3	Adjustment #2 (if needed)	Adjustment #3 (if needed)	Lock-in #1	Lock-in #2 (if needed)	Post Lock-in	Postop Month 3	Postop Month 6 or later	Unscheduled Visit ³
Slit Lamp Exam	X		X	X	X	X	X	X	X	X	X	X	
Fundus Exam	X				X						X	X	
Aberrometry	X			X	X	X	X	X	X	X	X	X	
Dilated Pupil Diameter	X				X	X	X	X	X				
Adverse Events		X	X	X	X	X	X	X	X	X	X	X	X

¹ Only performed on subjects with both eyes enrolled and successfully implanted

^{1.1} Only performed on subjects with both eyes enrolled and successfully implanted and subject did not have an [REDACTED] visit

² May be performed on a subgroup of subjects as described in section 7.3.2.2 of the protocol

³ Tests indicated with an "X" must be performed at each unscheduled visit. Other tests may be conducted based on the investigator's assessment of the subject.

⁴ Only required for subjects who previously participated in RxSight's CSP-037-MX study

⁵ Only performed on subjects who did not have an [REDACTED] visit

*Visits only required for subjects who did not previously participate in RxSight's CSP-037-MX study

** Subgroup of eyes based on decision made by Principal Investigator

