4 STUDY DESIGN

A prospective, single center, exploratory study will be conducted. Subjects will be followed until completion of the Postop Month 6 or later follow-up visit.

Patients who require cataract extraction and intraocular lens implantation will be pre-screened for eligibility as part of pre-entry activity. If one or both eyes meet inclusion/exclusion criteria, delegated and trained study staff will explain the study purpose, procedures, risks/benefits and subject responsibilities to the potential participant. Written informed consent must be obtained prior to initiation of any clinical procedures that are performed solely for the purpose of determining eligibility for research. The patient is enrolled upon signing the informed consent. Both eyes of all subjects may be screened for eligibility at the same preoperative visit. If at any time during the preoperative visit, an eye does not meet inclusion or exclusion criteria, screening for that eye can be discontinued immediately. If only one eye is being screened, then the subject will be exited from the study. If both eyes of the subject are enrolled for study participation, each eye will be scheduled for surgery within a timeframe of the investigator's choice but on separate days.

Patients from RxSight's CSP-037-MX study may have both eyes screened for study eligibility. The former CSP-037-MX study eye must meet all inclusion/exclusion criteria as specified below for subjects who previously participated in CSP-037-MX. If applicable, the fellow eye (CSP-037-MX non-study eye) must meet all inclusion/exclusion criteria as specified below for subjects who did not previously participate in CSP-037-MX. If only the prior CSP-037-MX study eye is being considered for this study, the subject will need to review and sign only a CSP-036-MX written informed consent for former CSP-037-MX subjects. If both eyes are being considered for this study, the subject will also have to review and sign a CSP-036-MX written informed consent for subjects who had no affiliation with CSP-037-MX.

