7.2 SUBJECT ENTRY

Patients who require cataract extraction and intraocular lens implantation will be pre-screened for eligibility as part of pre-entry activity. If one or both eyes meet inclusion/exclusion criteria, delegated and trained study staff will explain the study purpose, procedures, risks/benefits and subject responsibilities to the potential participant. Written informed consent must be obtained prior to initiation of any clinical procedures that are performed solely for the purpose of determining eligibility for research. The patient is enrolled upon signing the informed consent. The subject will sign and date the informed consent form in the presence of the person conducting the consent process. The investigator and/or the person conducting the consent process will also sign and date the consent form. During the study, the subject will be provided with any new information that is received that could affect their health status or change their willingness to continue to participate in the study. Both eyes of all subjects may be screened for eligibility at the same preoperative visit. If at any time during the preoperative visit, an eye does not meet inclusion or exclusion criteria, screening for that eye can be discontinued immediately. If only one eye is being screened, then the subject will be exited from the study. The preoperative examination will be performed no more than 60 days prior to surgery. If the 60-day time period elapses, it is acceptable for patients to be re-screened by undergoing a complete preoperative examination. Ocular dominance testing will be performed as part of the preoperative evaluation to determine eye dominance. If both eyes of the subject are enrolled for study participation, each eye will be scheduled for surgery within a timeframe of the investigator's choice but on separate days.

Only subjects meeting all inclusion/exclusion criteria will be implanted. Those subjects who do not meet the inclusion/exclusion requirements will be considered screen failures. Unique identification numbers will be assigned to each subject.

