7.3.2.2 Additional Clinical Testing

Additional clinical testing may be performed on a subgroup of study subjects. The Principal Investigator may determine whether a subject will be included into a clinical test subgroup based on the adjustment light treatments to be performed. Clinical measurement subgroups will include:

- Undilated photopic pupil diameter (Week 3, Post Lock-In, Month 3, Month 6 or later)
- Binocular UCDVA, UCIVA, UCNVA (Week 3, Post Lock-In, Month 3, Month 6 or later)
- Depth of Focus (Week 3, Lock-In #1, Post Lock-In, Month 3, Month 6 or later)
- Monocular DCIVA, DCNVA, UCIVA, UCNVA (Week 3, Lock-In #1, Post Lock-In, Month 3, Month 6 or later)
- Monocular Distance Corrected Contrast Sensitivity (Photopic/Mesopic) (Week 3, Post Lock-In, Month 3, Month 6 or later)
- [REDACTED]
- Posterior Segment SD-OCT

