8.1.1 EXPLORATORY EFFECTIVENESS PARAMETERS

Primary Exploratory Parameters

Eyes that received only non-presbyopic adjustments.

- % of eyes with UCDVA of 20/20 or better at Postop Month 6 or later

Eyes that received a presbyopia adjustment.

- Proportion of eyes simultaneously with (1) Monocular UCDVA of 20/25 or better and (2) Monocular UCIVA of 20/32 or better and (3) Monocular UCNVA of 20/40 or better at Postop Month 6 or later.

Clinical data for former CSP-037-MX study eyes may be analyzed separately.

Additional Exploratory Parameters

UCDVA

Monocular and/or binocular UCDVA will be presented with the number and percent of eyes that fall into each category of visual acuity performance (e.g. 20/20 or better, 20/25 or better, 20/32 or better, etc.) at each visit tested. Number and percent for eyes that only received non-presbyopic adjustments and for eyes that received a presbyopia adjustment may be presented separately. In addition, clinical data for former CSP-037-MX study eyes may be analyzed separately.

UCIVA, UCNVA, DCIVA, and DCNVA

Monocular and/or binocular UCIVA, UCNVA, DCIVA, and DCNVA for eyes that received a presbyopia adjustment will be presented with the number and percent of eyes that fall into each category of visual acuity performance (e.g. 20/20 or better, 20/25 or better, 20/32 or better, etc.) at each visit tested. In addition, clinical data for former CSP-037-MX study eyes may be analyzed separately.

Depth of Focus

The mean acuity across all eyes that received a presbyopia adjustment will be calculated and plotted separately. The mean, standard deviation, and confidence intervals for each point on the curve will be reported. In addition, clinical data for former CSP-037-MX study eyes may be analyzed separately.

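### Optional binocular acuity tests carry no condition on the fellow eye's adjustment or lock-in, so one visit label in the binocular tables can mix treatment states and count a subject twice

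*Combined protocol and SAP*

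**What the plan says.** **Who is tested.** In section 7.5, Table 1, footnote 1 reads "Only performed on subjects with both eyes enrolled and successfully implanted". Footnote 1.1 adds only that the subject did not have a certain redacted visit. From Week 3 onward the binocular distance acuity cells also carry footnote 2: "May be performed on a subgroup of subjects as described in section 7.3.2.2 of the protocol". Section 7.3.2.2 explains that subgroup: "The Principal Investigator may determine whether a subject will be included into a clinical test subgroup based on the adjustment light treatments to be performed". None of these mentions the state of the fellow eye.

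**When.** Section 7.3.2.2 places binocular distance, intermediate and near acuity at Week 3, Post Lock-in, Month 3 and Month 6 or later. The windows in section 7.4 are counted from surgery or from the preceding light treatment, for example "Days 17 to 30 days postop: Adjustment #1". Section 9.2 counts completion of the Month 6 visit by eye.

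**Gap between surgeries.** Section 4 says "each eye will be scheduled for surgery within a timeframe of the investigator's choice but on separate days". No maximum is given. The 60-day preoperative window does not supply one, because section 7.2 allows re-screening: "If the 60-day time period elapses, it is acceptable for patients to be re-screened by undergoing a complete preoperative examination".

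**Analysis.** Section 8.1.1 says "Monocular and/or binocular UCDVA will be presented with the number and percent of eyes" in each acuity category, for every visit at which it was measured. Intermediate and near acuity are handled the same way for presbyopia-adjusted eyes. There is no restriction on the fellow eye, and no statement of whose calendar names the visit.

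**The concern.** A binocular result belongs to a pair of eyes, but the visit label attached to it describes only one of them. If the two surgeries are staggered, a test at the first eye's Post Lock-in visit may include a second eye that has not been locked in. A Week 3 test on the second eye's calendar may include a first eye that has already been treated.

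Staggering is foreseeable. A former CSP-037-MX subject enters with one eye already implanted and may enrol the other for later surgery.

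Two things are at stake in the binocular tables. A row for one visit can combine pairs in different treatment states. Also, because results are expressed as percent of eyes and both eyes pass through a visit of the same name, one subject can appear twice in a row, possibly in two different states. Section 10.6 says that vision can change unpredictably if a lens is exposed to daylight or another UV source before lock-in, so the distinction is not merely one of labelling.

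**Working it through.** The plan gives no figure to reproduce here; the check is day arithmetic on its own windows.

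**Inputs (sections 7.3.2 and 7.4)**
- Adjustment #1: Day 17 to 30 after that eye's surgery.
- One to three adjustments and one or two lock-ins, each 2 to 7 days after the previous light treatment.
- Post Lock-in: 7 to 14 days after the final lock-in.
- Month 3: Day 90 to 150. Month 6 or later: Day 180 to 400.

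**Calendar of one eye**
- Earliest final lock-in (one adjustment, one lock-in): 17 + 2 = Day 19.
- Latest (three adjustments, two lock-ins): 30 + 7 + 7 + 7 + 7 = Day 58.
- Post Lock-in: from 19 + 7 = Day 26 to 58 + 14 = Day 72.

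**Test on the first eye's calendar**

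Let G be the gap in days between surgeries and D the first eye's postoperative day. The fellow eye is then at its own day D − G.
- Footnote 1 bars the test until the second eye is implanted. Requiring D − G ≥ 1 gives G ≤ D − 1.
- The fellow eye is certainly not locked in if D − G ≤ 18, that is G ≥ D − 18.
- It can still be unlocked if D − G ≤ 57, that is G ≥ D − 57 (and at least 1).

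| First-eye visit | D | Certainly not locked in, G | Can be not locked in, G |
|---|---|---|---|
| Post Lock-in, earliest | 26 | 8 to 25 | 1 to 25 |
| Post Lock-in, latest | 72 | 54 to 71 | 15 to 71 |
| Month 3, earliest | 90 | 72 to 89 | 33 to 89 |
| Month 6, earliest | 180 | 162 to 179 | 123 to 179 |

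Every range has an upper end. Beyond it the second eye is not yet implanted and footnote 1 removes the test.

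**Do the Month 6 gaps fit the study?** The synopsis gives about 6 to 12 months of participation per subject. Taking 12 months as 365 days, a second eye reaching its Day 180 within that time implies G ≤ 365 − 180 = 185 days. This is a soft limit, and it lies above 179. For example, with G = 170 the first eye's Day 180 is the fellow eye's Day 10, and the fellow eye's own Day 180 falls on 170 + 180 = Day 350.

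**Test on the second eye's calendar**

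The second eye's Week 3 visit is at its Day 17 at the earliest, which is the first eye's Day G + 17. The first eye's Adjustment #1 is in window by Day 30. It has certainly gone before when G + 17 > 30, that is G ≥ 14. This condition has no upper end, because both eyes are by then implanted.

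**The case against.** Several points on the other side stand.

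- **The tests are optional.** A reader might infer that implantation of both eyes is the sole condition and that a site will necessarily record mixed-state values. Footnote 2 and section 7.3.2.2 do not support that. The investigator selects the subgroup and could avoid such cases. What remains is that nothing requires it.
- **Longer gaps do not keep making it worse.** One might argue that a mixed state at the first eye's Post Lock-in visit is certain for every gap beyond 53 days. That ignores footnote 1: from a gap of 72 days no in-window Post Lock-in test on the first eye's calendar is allowed. Nor is the gap strictly unlimited, given the approximate participation time.
- **Parts are inferred.** No sentence says that binocular tests follow each eye's own calendar; this is read from the windows and section 9.2. The binocular intermediate and near rows of Table 1 are not in the text I had, nor is Appendix 1, which section 11 cites for examination procedures. A condition could stand there.
- **Week 3 is not called a baseline.** Footnote 1.1 also drops that test for subjects who had the redacted visit at Days 7 to 14. Because the content of that visit is hidden, I say only that the fellow eye is not locked in, not that it is untreated.
- **The impact is limited.** A reader might infer that the study could no longer show what the adjustments achieve. The primary exploratory parameters are eye-level, the presbyopia composite is expressly monocular, and no binocular before-and-after comparison is planned. Treatment dates should allow the fellow eye's state to be derived later.

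None of this supplies the missing rule. Gaps of 8 to 25 days fall within what section 4 permits, and the second-eye Week 3 case has no upper limit on the gap.

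**Conclusion.** The concern holds as a minor point. As written, the plan lets binocular results in different treatment states share a visit label, and lets one subject contribute twice to a row expressed in eyes. The gap ranges above assume in-window treatment and that each eye keeps its own visit calendar. Postponements under section 7.3.2.1 can push a fellow eye's lock-in past Day 58 and widen the first-eye ranges; a delayed Adjustment #1 in the first eye would raise the 14-day figure.

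How many subjects would be affected cannot be computed, because the documents give neither the distribution of surgery gaps nor the size of the tested subgroup. The consequence is confined to additional exploratory, descriptive summaries of binocular acuity, and possibly a redacted Table 1 row that carries the same footnotes. The conclusion would change if Appendix 1 already sets a condition on the fellow eye; in that case the footnotes should cite it.

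**What to change.** - **Footnotes 1 and 1.1 and section 7.3.2.2:** take the Post Lock-in, Month 3 and Month 6 binocular tests at the visits of whichever eye is locked in last, so that both eyes have had their final lock-in.
- **Labelling:** call a binocular value pre-adjustment only if neither eye has yet received a light treatment.
- **Section 8.1.1:** report binocular acuity per subject, with one value per visit, instead of as percent of eyes. Show any values already taken in a mixed state separately, by the fellow eye's status, and do not discard them.

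The cost is a change to footnote wording and a sentence or two in the analysis section. The downside is fewer binocular values at first-eye visits, and fewer pre-adjustment values where surgeries are far apart. No change to surgery timing or treatment is proposed.

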7.6 DATA REPORTING

All study data will be recorded onto case report forms (electronic or paper) designed for the study. CRFs can be signed by the investigator either by paper signature or by electronic signature. The CRF may be the source document for some data and each site will document this with a note to file describing in which cases source data will be recorded directly onto the CRF. If paper CRFs are used, all CRFs will be completed in a legible manner in black/blue ink.

Any corrections to the CRFs will be made by drawing a single line through the incorrect entry, recording the correct information, and initialing and dating the change. The CRFs and/or data entered in the EDC system will be reviewed by the Study Monitor.

All clinical data generated in the study will be submitted to RxSight or designated CRO for quality assurance review and statistical analysis. All CRFs and/or data entered into the EDC system will be reviewed for completeness and evident recording errors will be rectified by contact with the appropriate clinical site. Computerized data checks if applicable will be used to identify unusual data entries for verification prior to statistical analysis.

To minimize the amount of missing data, investigators will be trained on the deleterious effect that missing data have on trial integrity and credibility and that missing data could diminish the scientific value of all subjects' altruistic contributions.

